8.7. Study Size

The sample size for this study is fixed by the number of people meeting the inclusion criteria during the observation period. No formal sample size computation was performed. All patients who meet inclusion/exclusion criteria will be included in the analyses.

8.8. Data Management

The MarketScan Research Databases comply with both the spirit and the letter of the Health Insurance Portability and Accountability Act of 1996 (HIPAA). The MarketScan Databases meet the criteria for a limited-use dataset and contain none of the data elements prohibited by HIPAA for limited-use datasets.

8.9. Data Analysis

8.9.1. Primary and Secondary Analyses

Descriptive and multivariate regression analyses will be performed to satisfy the primary and secondary analyses as described in Table 4. Details on the descriptive and multivariate methods follow in [Section 8.9.2](#) and [Section 8.9.3](#) respectively.

Table 4. Primary and Secondary Objectives for Comparison Between MR 11 mg QD and IR 5 mg BID.

Endpoint	Objective	Type	Post Index Duration	Analysis ^a
Effectiveness ^b (algorithm defined)	Primary	Dichotomous	12 months	Generalized linear model
Effectiveness ^c (duration of persistence)	Primary	Continuous	12 months	Cox regression
Adherence (MPR)	Primary	Continuous	12 months	Generalized linear model
Adherence (MPR ≥80%)	Primary	Dichotomous	12 months	Logistic regression
Adherence (PDC)	Primary	Continuous	12 months	Generalized linear model
Adherence (PDC ≥80%)	Primary	Dichotomous	12 months	Logistic regression
Effectiveness (duration of persistence)	Secondary	Continuous	6 months	Cox regression
Adherence (MPR)	Secondary	Continuous	6 months	Generalized linear model
Adherence (MPR ≥80%)	Secondary	Dichotomous	6 months	Logistic regression

Table 4. Primary and Secondary Objectives for Comparison Between MR 11 mg QD and IR 5 mg BID.

Endpoint	Objective	Type	Post Index Duration	Analysis ^a
Adherence (PDC)	Secondary	Continuous	6 months	Generalized linear model
Adherence (PDC ≥80%)	Secondary	Dichotomous	6 months	Logistic regression

a. Analyses will be repeated stratifying by number of previous advanced treatments (0, 1, and 2+ prior) if feasible.

b. The proportions of patients not meeting each of the 6 criteria separately will be described.

CCI

8.9.2. Descriptive Analysis

All study variables, including pre- and post-index measures, will initially summarized descriptively. In general, numbers and percentages will be provided for dichotomous and polytomous variables, while means, medians, and standard deviations will be provided for continuous variables. Missing or unavailable data will not be imputed.

Results will be stratified by treatment cohort, bivariate comparisons of pre- and post-index measures will be provided, and appropriate tests (eg, t-test, Mann Whitney-U test, chi-square test) will be used based on the distribution of the measure. The analysis that is performed (ie, the methods that are used and the patients who are included) will be specific the objective being examined. Descriptive techniques will be implemented for each objective.

8.9.3. Multivariate Analysis

To control for possible confounding of the relationship between the outcomes and independent variable of interest multivariable (logistic, generalized linear, and Cox) regression models will be evaluated as described in [Table 4](#).

The models will include insurance type, region, age, sex, prior advance therapies in variable length period (None, 1 and 2+) as covariates. The following variables will be evaluated for inclusion as a covariate and be included if differences between MR 11 mg QD and IR 5 mg BID at baseline with $p < 0.10$: 12-month pre-index use (% and means) of csDMARD, opioids, corticosteroids and presence of comorbidities including, cardiovascular disease, chronic obstructive pulmonary disease (COPD), asthma, kidney disease, depression, anxiety, liver disease, sleep disorders, hypertension, hyperlipidemia, Quan-Charlson comorbidity index and CIRAS scores, rheumatologist visit count during 1-year pre-index, disease duration, pre-index total costs, length of pre-index period, use of advanced therapy in 12 month pre-index and presence of csDMARD in 90 days post-index.

Generalized linear models (GLM) will be fit, using appropriate distributions and links for the nature of the data (eg, normally-distributed data with identity link, binary data and logit link). Point estimates, 95 percent confidence intervals, and p-values will be presented for contrasts; analysis of variance table will be presented to display the strength of the independent

variables, including point estimates and p-values. If there are problems with model fit, for example, failure to converge, transformation of data may be used in order to try a different distribution and link.

CCI [REDACTED]

[REDACTED]

[REDACTED]

[REDACTED]

[REDACTED]

[REDACTED]

[REDACTED]

[REDACTED]

[REDACTED]

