Combination therapy, 90 days post-index (including index)	Baseline Clinical Characteristics	Combination therapy defined as first comedication with any csDMARD (Annex 2) within 90 days on or after the index date. Classify first csDMARD as methotrexate, leflunomide, hydroxychloroquine, sulfasalazine or other. If more than 1 csDMARD on same day, note methotrexate plus other or if not with methotrexate, just classify as >1 csDMARD other than methotrexate. Monotherapy defined as the complement to combination therapy.
Quan-Charlson comorbidity score, continuous, 12-month pre-index	Baseline Clinical Characteristics	A weighted scale of 17 co-morbidities (based on associated diagnosis codes on medical claims in the 12-months pre-index) presented as a summative score to evaluate co-morbid chronic illness burden.
Quan-Charlson comorbidity score, categorical 12-month pre-index	Baseline Clinical Characteristics	The continuous Quan-Charlson comorbidity score categorized into: 0, 1-2, 3-4, 5+ QCCI comorbidities (Annex 3). ^{4,9}
Opioid, non-steroidal anti-inflammatory drug (NSAID) use, dichotomous, 12-month pre-index	Baseline Clinical Characteristics	The use of weak and/or strong opioids and/or non-steroidal anti-inflammatory drug (NSAID) (Annex 2) during the 12-month pre-index periods.
Opioid, non-steroidal anti-inflammatory drug (NSAID) use, continuous 12 month pre-index	Baseline Clinical Characteristics	The number of pharmacy claims for weak and/or strong opioids and/or non-steroidal anti-inflammatory drug (NSAID) (Annex 2) during the 12-month pre-index periods.

Table 2. Variables Used in Analyses

Variable	Role	Operational definition
Pre-index corticosteroids, dichotomous	Baseline Clinical Characteristics	The use of oral corticosteroids (Annex 2) during the 12-month pre-index.
Pre-index corticosteroid total exposure/dose, continuous, 12-month pre-index	Baseline Clinical Characteristics	The total prednisone-equivalent dose of oral corticosteroids in the 12 months prior to index, defined as: the sum of prednisone equivalent dose (Strength*quantity/equivalence factor) of a filled corticosteroid. (Dose equivalent factors: Betamethasone=0.6, Dexamethasone=0.75; Methylprednisolone, Triamcinolone=4, Prednisone, Prednisolone=5; Hydrocortisone=20, Cortisone=25; Fludrocortisone=n/a).

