Visit with a rheumatologist in 90 days prior to index, dichotomous	Baseline Clinical Characteristics	At least one ambulatory visits (office visit or outpatient visit) in which the physician was a rheumatologist in the 90 days before or on the index date.
Visit with a rheumatologist in 12 months prior to index, dichotomous	Baseline Clinical Characteristics	At least one ambulatory visits (office visit or outpatient visit) in which the physician was a rheumatologist in the 12 months before or on the index date.
Visit with a rheumatologist in 12 months prior to index, continuous	Baseline Clinical Characteristics	Count of Ambulatory visits (office visit or outpatient visit) in which the physician was a rheumatologist in the 12 months before or on the index date.
Disease duration	Baseline Clinical Characteristics	The number of days from the earliest claim with a diagnosis of RA in the variable length baseline until the index date.
Total all-cause costs, 12-month pre-index, continuous	Baseline Clinical Characteristics	Sum of patient and plan paid costs for all healthcare resource use in 12 month pre-index period. CPI adjusted to 2018 dollars (http://data.bls.gov/cgi-bin/surveymost?cu U.S. Medical Care, 1982-84=100 - CUUR0000SAM).
Comorbidities, 12 month pre-index, dichotomous Cardiovascular diseases Chronic obstructive pulmonary disease (COPD) Asthma Kidney disease Diabetes Depression Anxiety Liver disease Sleep disorders Hypertension Hyperlipidemia	Baseline clinical characteristics	Presence or absence of codes for the comorbidities of interest during the 12-months prior to index (Annex 2).

Table 2. Variables Used in Analyses

Variable	Role	Operational definition
Pre-index Claims-based index for RA severity (CIRAS), 12 month pre-index, continuous	Baseline clinical characteristic	The Claims-based Index for RA Severity will be implemented. CIRAS provides a single value of severity using the following 9 measures: age, gender, inflammatory marker tests, rehabilitation visits, Felty Syndrome, platelet orders, rheumatoid factor tests, chemistry panels, and rheumatologist visits. Scores range from 0 (low) to 10 (high)(Annex 4). ¹⁰
Length of variable length pre-index period, continuous	Baseline characteristic	The period from start of continuous enrollment through index without gaps in coverage.

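### Beyond five forced covariates, measured confounders enter the models only if the MR-IR baseline difference has p<0.10, so some measured confounding may remain in the primary and secondary contrasts

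*Combined protocol and SAP*

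**What the plan says.** Section 8.9.3 (Multivariate Analysis) gives the regression models the purpose of controlling confounding and sorts the covariates into two groups.

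- **Forced:** "The models will include insurance type, region, age, sex, prior advance therapies in variable length period (None, 1 and 2+) as covariates".
- **Screened:** the remaining listed variables are to "be included if differences between MR 11 mg QD and IR 5 mg BID at baseline", with p<0.10 as the threshold. They are csDMARD, opioid and corticosteroid use, ten named comorbidities, Quan-Charlson, CIRAS, rheumatologist visit count, disease duration, total costs, length of the pre-index period, advanced therapy use in the prior 12 months, and csDMARD presence in the 90 days after index.

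The named comorbidities are "cardiovascular disease, chronic obstructive pulmonary disease (COPD), asthma, kidney disease, depression, anxiety, liver disease, sleep disorders, hypertension, hyperlipidemia". The matching row of Table 2 (Section 8.5) has eleven and includes diabetes: "Kidney disease Diabetes Depression Anxiety Liver disease Sleep disorders Hypertension Hyperlipidemia". For medications, Section 8.9.3 lists "12-month pre-index use (% and means) of csDMARD, opioids, corticosteroids and presence of comorbidities including" the comorbidities, without NSAIDs. Table 2 measures them in one variable with opioids: "The use of weak and/or strong opioids and/or non-steroidal anti-inflammatory drug (NSAID) (Annex 2) during the 12-month pre-index periods".

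Section 8.7 states that no sample size was computed and that the cohort is whatever meets the criteria. Table 4, footnote a, repeats the analyses by number of prior advanced treatments if feasible.

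**The concern.** A covariate confounds the MR-IR contrast to the extent that it is imbalanced between cohorts and also related to outcome. A baseline p-value reflects only the first of these, and mixes it with sample size. A strongly prognostic variable with a moderate imbalance can be left out, while an irrelevant one with a clear imbalance is kept. Because the cohort size is not fixed, the same imbalance may be adjusted for in one data cut and not in another. The prior-therapy strata are smaller, and the plan does not say whether the screen is rerun in them.

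The plan itself ties some screened variables to a primary endpoint. In Table 2, pre-index oral glucocorticoid use decides which branch of effectiveness criterion 5 applies, and the pre-index dose is the comparator in one branch. Pre-index csDMARD claims help define what counts as an addition under criterion 4. Both can be dropped from the effectiveness model because of a baseline p-value.

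At stake is avoidable bias in a non-randomised comparison, in either direction.

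**Working it through.** The documents give no cohort size, imbalance or covariate-outcome association, so there is no planned figure to reproduce. From the plan come the p<0.10 threshold, the two covariate groups and the absence of a fixed N. Every other input below is an assumption.

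**1. Chance that the screen misses a real imbalance.** For a binary covariate with prevalences p1 and p2 and n per arm, SE = √[(p1(1−p1) + p2(1−p2))/n], and the miss probability is 1 − Φ(|p1−p2|/SE − 1.645). For 20% vs 25% with n = 500: SE = √(0.3475/500) = 0.0264, 0.05/0.0264 = 1.90, and 1 − Φ(0.25) = 0.40.

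| n per arm | 20% vs 25% | 20% vs 23% |
|---|---|---|
| 200 | 0.67 | 0.82 |
| 500 | 0.40 | 0.69 |
| 1000 | 0.15 | 0.50 |
| 2000 | 0.02 | 0.25 |

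The imbalance is the same down each column; only N changes.

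**2. Effect of one omitted covariate.** In a linear model, a covariate just failing the screen shifts the contrast by 1.645 × ρ standard errors, where ρ is its correlation with outcome. The type I error is P(|Z + shift| > 1.96).

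- ρ = 0.1: shift 0.16 SE, type I error 0.053.
- ρ = 0.3: shift 0.49 SE, type I error 0.078.
- Five independent covariates with ρ = 0.1, all at the boundary and in the same direction: 5 × 0.164 = 0.82 SE, type I error 0.130.

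**3. Many covariates together.** The simulation has no true effect and 18 independent binary confounders, each 30% vs 34% and each with outcome odds ratio 1.3. It uses logistic models and 300 data sets per setting. All confounders push the same way.

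| n per arm | Confounders dropped | OR after screen | OR, all covariates |
|---|---|---|---|
| 300 | 72% | 1.07 | about 1.00 |
| 600 | 56% | 1.06 | about 1.00 |
| 1000 | 39% | 1.03 | about 1.00 |

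An approximation agrees. The log odds ratio left behind is (number dropped) × (mean imbalance among those dropped) × ln 1.3, where ln 1.3 = 0.262. Dropped covariates have a smaller observed imbalance than 4 points because they failed the test.

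- n = 300: 12.96 × 0.0229 × 0.262 = 0.078, OR 1.08.
- n = 600: 10.12 × 0.0213 × 0.262 = 0.056, OR 1.06.
- n = 1000: 7.05 × 0.0196 × 0.262 = 0.036, OR 1.04.

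With no adjustment the figure is 18 × 0.04 × 0.262 = 0.189, OR 1.21 (about 1.18 to 1.20 in simulation), so the screen removes most of the assumed bias but not all.

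With nine confounders favouring each arm, the drop rates are about the same (72%, 57%, 39%), but the screened OR is about 1.00 at all three sizes.

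**4. A covariate never offered to the model.** Bias on the risk scale = imbalance × effect on outcome risk. An imbalance of 2 to 10 points and an effect of 5 to 15 points give 0.02 × 0.05 = 0.1 up to 0.10 × 0.15 = 1.5 percentage points.

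**The case against.** The strongest reply is that the practical effect is small. Step 3 gives a visible bias only when all the confounders line up. Even then, type I error at 300, 600 and 1000 per arm was 0.078, 0.056 and 0.072 with the screen, against 0.066, 0.040 and 0.050 with full adjustment (Monte Carlo error about 0.01). The root mean squared error of the log odds ratio hardly moved (0.186 vs 0.185, 0.131 vs 0.123, 0.098 vs 0.093). Only a logistic model was simulated, without forced covariates or correlation between confounders, so the result does not carry over directly to the Cox and continuous models. This stands, and it limits the size of the point.

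On the omissions, diabetes contributes to Quan-Charlson (Annex 3, weight 1 without and 2 with chronic complications), though only if that score passes the screen. The comorbidity list is introduced as inclusive and need not be exhaustive, and opioids may be shorthand for the combined Table 2 variable. A reader might infer that diabetes and NSAID use are certainly unadjusted; the text supports only a mismatch between two lists.

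A reader might also infer that regression is the only protection against confounding. It is not. The design requires RA and prior methotrexate, excludes other indications and index-drug use in the prior year, compares two formulations stated to cost the same, and plans stratified repeats. Nor can one say that no further adjustment analysis exists, since text after the GLM paragraph is redacted. The entry rule itself is legible, however, and redacted additions would not change it for the Table 4 models.

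Putting overlapping variables in together (Quan-Charlson beside its components, CIRAS beside age and sex) makes their own coefficients hard to read, but does not bias the MR-IR contrast.

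**Conclusion.** The point holds as a modest, cheaply avoidable weakness. The p<0.10 rule is a poor criterion for confounding control: it depends on an unfixed N and disregards outcome, and it governs the severity index and variables built into the algorithm endpoint. Measured confounding may remain. The documents do not show that it will, because they give no imbalance or outcome association. The illustrative spurious odds ratio of about 1.03 to 1.07 rests on assumed cohort sizes and on 18 confounders acting in one direction; with mixed directions it is about 1.00.

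Two stronger readings are not supported. It is not true that every confounder must pass the screen, since five covariates, including prior advanced therapy, are forced. Nor is it shown that standard errors are invalid because of selection: the screen does not use the outcome, and in the mixed-direction runs type I error with the screen (0.044, 0.052, 0.068) was no higher than with full adjustment (0.052, 0.056, 0.072).

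**What to change.** In Section 8.9.3:

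1. Delete the p<0.10 entry rule.
2. Prespecify the listed pre-index covariates, plus diabetes and the Table 2 opioid/NSAID variable, in every Table 4 model regardless of baseline p-value. This also brings the candidate list into line with Table 2.
3. Report standardised differences between cohorts for description only, not for selection.
4. State separately how csDMARD presence in the 90 days after index is handled. It is measured after treatment starts and should not be treated as a baseline covariate by default.
5. For small prior-therapy strata, prespecify one reduced list, or a propensity score built from the full list.

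The cost is protocol or SAP wording and a few more degrees of freedom, with some overlap among adjustment variables and slightly wider intervals in small strata. The variables in item 2 are already defined in Table 2; a separate NSAID variable would need a new definition, which is why the combined one is used.

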8.10. Quality Control

This is a retrospective study, so issues of quality control at study sites, eg, data queries, do not apply. Analyses are programmed according to the specifications in the protocol, and if applicable, the statistical analysis plan, and documented in a programming plan. Final deliverables are reviewed and verified by a second, independent programmer who may also perform double programming. All quality checks are documented in the programming plan.

8.11. Limitations of the Research Methods

Limitations that are general to claims database analyses and specific to this study should be noted. First, diagnosis of autoimmune conditions will be identified using ICD-10-CM diagnosis codes, which are subject to potential miscoding, though presumably without respect to the treatment or outcomes. Second, the baseline period for this study will generally be 12 months long. Therefore, patients treated with a bDMARD or tofacitinib in the baseline can be considered to be prior users of therapy; however, patients with no bDMARD or tofacitinib use in the baseline may have just been off therapy for the 12 months prior. Lastly, this study will include an examination of medication effectiveness at 1 year among all bDMARD and tofacitinib users. Effectiveness (yes/no) will be measured using a validated algorithm; however, the algorithm was not validated for all medications being included. Specifically, tofacitinib was approved for treatment of RA after the algorithm was developed. This study will include consultation with physicians to determine if the algorithm is valid for all study medications or if modifications need to be implemented.

8.12. Other Aspects

Not applicable.

9. PROTECTION OF HUMAN SUBJECTS

9.1. Patient Information

All parties will comply with all applicable laws, including laws regarding the implementation of organizational and technical measures to ensure protection of patient personal data. Such measures will include omitting patient names or other directly identifiable data in any reports, publications, or other disclosures, except where required by applicable laws.

To protect the rights and freedoms of natural persons with regard to the processing of personal data, when study data are compiled for transfer to Pfizer and other authorized parties, any patient names will be removed and will be replaced by a single, specific, numerical code. All other identifiable data transferred to Pfizer or other authorized parties will be identified by this single, patient-specific code. In case of data transfer, Pfizer will maintain high standards of confidentiality and protection of patients' personal data consistent with the vendor contract and applicable privacy laws.

9.2. Patient Consent

As this study does not involve data subject to privacy laws according to applicable legal requirements, obtaining informed consent from patients by Pfizer is not required.

9.3. Institutional Review Board (IRB)/Independent Ethics Committee (IEC)

IRB is not required for this study as it uses commercially available de-identified secondary data sources and is considered exempt from the requirements for "human subjects research" in the US.

9.4. Ethical Conduct of the Study

The study will be conducted in accordance with legal and regulatory requirements, as well as with scientific purpose, value and rigor and follow generally accepted research practices described in CT24-WI-GL02-RF04 and the International Society for Pharmacoeconomics and Outcomes Research (ISPOR).

10. MANAGEMENT AND REPORTING OF ADVERSE EVENTS/ADVERSE REACTIONS

This study involves data that exist as structured data by the time of study start or a combination of existing structured data and unstructured data, which will be converted to structured form during the implementation of the protocol solely by a computer using automated/algorithmic methods, such as natural language processing.

In these data sources, individual patient data are not retrieved or validated, and it is not possible to link (ie, identify a potential association between) a particular product and medical event for any individual. Thus, the minimum criteria for reporting an adverse event (AE) (ie, identifiable patient, identifiable reporter, a suspect product, and event) cannot be met.

11. PLANS FOR DISSEMINATING AND COMMUNICATING STUDY RESULTS

For all publications relating to the Study, Pfizer will comply with recognized ethical standards concerning publications and authorship, including Section II - “Ethical Considerations in the Conduct and Reporting of Research” of the Uniform Requirements for Manuscripts Submitted to Biomedical Journals, <http://www.icmje.org/index.html#authorship>, established by the International Committee of Medical Journal Editors.

In the event of any prohibition or restriction imposed (eg, clinical hold) by an applicable competent authority in any area of the world, or if the party responsible for collecting data from the participant is aware of any new information which might influence the evaluation of the benefits and risks of a Pfizer product, Pfizer should be informed immediately.

